5 TRIAL SETTING

Imperial College Healthcare NHS Trust, St Mary's Hospital, London and Imperial College London

6 PARTICIPANT ELIGIBILITY CRITERIA

The trial population will be patients with a diagnosis of COPD who fulfil the inclusion/exclusion criteria outlined below

6.1 Inclusion criteria

Age 40-85 years

A clinical diagnosis of COPD confirmed with spirometry (Post-bronchodilator FEV₁/FVC <70%)

A smoking history of at least 15 pack years

Absence of infection for at least 8 weeks prior to study entry

No use of antibiotics and oral corticosteroids at least 8 weeks prior to study entry

Able to understand and consent to the study procedures

6.2 Exclusion criteria

Diagnosis of diabetes irrespective of treatment

Diabetes diagnosed on screening bloods

History of hepatic/renal impairment or hepatic/renal impairment diagnosed on screening bloods

Excessive alcohol intake (>21 units/week in males and >14 units in females)

BMI < 18.5kg/m²

Taking metformin irrespective of indication

History of allergy or hypersensitivity to metformin or hypersensitivity or intolerance to any of the placebo compounds

Pregnancy or breastfeeding

Unable to provide informed consent

Any contraindication for Metformin treatment as detailed in Metformin SmPC including:

Acute conditions with the potential to alter renal function such as dehydration, severe infection, shock

Acute or chronic disease which may cause tissue hypoxia such as cardiac or respiratory failure, recent myocardial infarction, shock

Any type of acute metabolic acidosis

7 TRIAL PROCEDURES

All subjects will have clinical assessments and blood, airway samples (nasal SAM and sputum) collected at baseline prior to the treatment phase. Clinical assessments will include lung function (FEV₁ and FVC), quality of life and symptom questionnaires (St George's Respiratory Questionnaire, COPD assessment test). Women of childbearing potential will only be included after a confirmed menstrual period and a negative highly sensitive urine pregnancy test. Subjects will then either be commenced on metformin or placebo for a period of 3 months and blood, sputum and nasal samples collected at monthly intervals. Following a 2 week washout period the subjects will crossover to the other study arm for another 3 months and repeat samples collected.

7.1 Recruitment

The study will be carried out in conjunction with the clinical team at Imperial College Healthcare NHS Trust. The PI is part of this team. Potential participants will be identified from COPD patients attending the clinical service. The applicant will identify potential participants.

7.1.1 Participant identification

Potential participants will be identified from COPD patients attending the clinical service. The PI who is part of the normal clinical team will identify potential participants and confirm eligibility.

7.1.2 Screening

A clinical diagnosis of COPD

7.1.3 Payment

A payment of £50 plus travel expense will be offered as compensation for the participants' time.

7.2 Consent

The PI will obtain informed consent from all participants. Potential participants will be provided with written information if they express an interest in participating in the study and given time to read this and discuss any questions that arise from this prior to providing informed consent. We will not recruit participants who have difficulties in adequately understanding written or verbal information in English.

7.2.1 Additional consent provisions for collection and use of participant data and biological specimens in ancillary studies, if applicable

Samples collected during the course of the study will be used for pre-specified analyses and any unused samples will be stored in an ethically approved research tissue bank for future specified or unspecified research. Participants will be asked for consent for use in future research related to the clinical condition under trial and may opt out but still participate in the main trial.

7.3 The randomisation scheme

Simple randomisation

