7.3.1 Method of implementing the randomisation/allocation sequence

The randomisation will be carried out using INFORM.

7.4

Blinding

The trial participants, care providers and outcome assessors will all be blinded. Randomisation will be the responsibility of the trial statistician and the medication will be dispensed in a blinded fashion from the hospital pharmacy. The trial medication will be over encapsulated. The final unblinding of all trial participants will occur at the end of the study after a close out visit and the creation of a locked analysis dataset.

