10 STATISTICS AND DATA ANALYSIS

10.1 Sample size calculation

The primary outcome will be change in sputum glucose from baseline after treatment with metformin, measured using an enzymatic assay (AmplexRed®). The median glucose concentration in COPD subjects measured in our previous study was 1,007 µM (SD 733µM). Metformin reduced airway glucose by c.30% in studies carried out in mice. Therefore to detect a similar effect in humans would require 30 subjects with 90% power at 5% significance. We aim to recruit 40 subjects to account for possible withdrawals.

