10.3.2 Primary outcome analysis

The primary endpoint (median sputum glucose in treated versus non-treated participants) will be analysed using a Mann-Whitney test. The post-treatment sputum glucose will also be compared with baseline glucose using Wilcoxon matched-pairs test. Similar methods will be used to analyse the secondary endpoints.

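### Simple randomisation of 40 people to two treatment orders, with no period term in the analysis, leaves the metformin-placebo estimate open to a period effect

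*Combined protocol and SAP*

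**What the plan says.** Section 7.3 consists of "Simple randomisation". Section 7.3.1 adds "The randomisation will be carried out using INFORM". No allocation ratio, blocking, stratification or reason for the choice is given.

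Section 7 makes this a two-sequence cross-over: "Subjects will then either be commenced on metformin or placebo for a period of 3 months", and then "Following a 2 week washout period the subjects will crossover to the other study arm for another 3 months". Randomisation therefore decides only which treatment comes first.

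Section 10.1 sets the numbers: "Therefore to detect a similar effect in humans would require 30 subjects with 90% power at 5% significance", and "We aim to recruit 40 subjects to account for possible withdrawals".

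Under section 10.3.2 the primary endpoint, treated against non-treated, "will be analysed using a Mann-Whitney test". A Wilcoxon matched-pairs test against baseline is added, and section 10.3.3 uses the same methods for the secondary outcomes. None of these has a term for period or sequence. Section 10.7 limits the analysis to the protocol-compliant population.

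**The concern.** In a two-period cross-over, a change between period 1 and period 2 that has nothing to do with treatment cancels from the simple treatment difference only if equal numbers take the treatments in each order. Otherwise it has to be removed in the analysis. This plan secures neither.

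The documents give some reason to expect a period effect, though none is measured. Section 6.1 requires at least 8 weeks free of infection, antibiotics and oral corticosteroids before entry. No matching condition is stated for the start of period 2, and sections 1 and 2 link airway glucose to bacterial infection. Period 1 thus starts from a selected state and period 2 need not (this is inference). Section 2 also describes exacerbations as worse in winter, and exacerbation count is a secondary endpoint.

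What is at stake is the effect estimate. Section 4 says that the pilot is meant to show how large any effect is, so that later trials can be powered. A shifted estimate would carry into those trials.

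**Working it through.** **Inputs.** Randomised: 40; required: 30 (section 10.1). Reference median 1,007 µM, SD 733 µM, reduction about 30% (section 10.1), so the target is 0.30 × 1,007 = 302 µM. Assumptions: 1:1 allocation, no carry-over, and a period effect π of 150 or 302 µM. The upper value is simply set equal to the target.

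**The plan's own figure.** The plan gives no figure for sequence balance. Its sample size of 30 does not follow directly from its inputs: (733 × (1.960 + 1.282) / 302.1)² = 61.9, so 62. It would need an SD of paired differences of about 510 µM, which means a within-person correlation of about 0.76. That is a separate issue. The correlation is used below only to set up a simulation.

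**Chance of imbalance.** With n1 ~ Binomial(N, 0.5), the chance of k:(N−k) or worse is 2P(X ≥ k).

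**Leak.** Add π to every period 2 value. The metformin-minus-placebo difference is then τ − π for those taking metformin first (n1) and τ + π for the others (n2). The unadjusted mean is τ + π(n2 − n1)/N, so the share of π that enters is |n1 − n2|/N.

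| Split, N = 40 | Chance of this or worse | Share of π | Shift, π = 150 µM | Shift, π = 302 µM |
|---|---|---|---|---|
| 24:16 | 26.8% | 20% | 30 µM | 60 µM |
| 25:15 | 15.4% | 25% | 38 µM | 76 µM |
| 26:14 | 8.1% | 30% | 45 µM | 91 µM |

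Exactly 20:20 occurs 12.5% of the time. The mean absolute difference between sequences is 5.0 people, so the average absolute share is 5.0/40 = 12.5%. With 30 analysed, 20:10 or worse has a 9.9% chance.

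**Over all randomisations.** The leak averages zero and its root mean square is 1/√40 = 15.8% of π. In simulation (4,000 trials per case, correlation 0.757, π = 302 µM) the mean error was near 0, and the SD of the estimate rose from about 81 µM at 20:20 to 93 µM under simple randomisation.

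**Tests.** With no true treatment effect and π = 302 µM, an unadjusted paired t-test rejected in 6.6% of simulated trials at 24:16 and 12.1% at 26:14. A period-adjusted test stayed at about 5%. The planned Mann-Whitney test, which ignores the pairing, rejected in under 1%.

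**If period is modelled.** The estimate is the average of the two sequence means, which is free of π at any split. Its variance relative to 20:20 is N²/(4·n1·n2). At 25:15 this is 1,600/1,500 = 1.067, or 7% more.

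**Blocking alone, after losses.** Suppose 10 of 40 are lost regardless of sequence. From simple randomisation the root-mean-square share is 1/√30 = 18.3%. From an exact 20:20, n1 among 30 completers is hypergeometric with variance 30 × 0.25 × 10/39 = 1.92, SD 1.39, and the share is 2 × 1.39/30 = 9.2%.

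**The case against.** The strongest reply is that the fault lies in the analysis rather than the randomisation. A period-adjusted comparison is valid at any split, and the precision then lost is small (7% at 25:15). This stands. It is wrong to infer that a cross-over needs equal sequences to be valid. But the plan does not contain the adjusted analysis, so the reply supports adding one and does not defend the present text.

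A reader might infer that the trial is biased. It is not, in the usual sense: over repeated randomisations the expected error is zero. The shift is conditional on the split obtained, although only one split will be obtained and reported.

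A reader might also infer a raised false-positive rate. The planned Mann-Whitney test is very conservative here, so the documents do not support that for the primary test. The leak formula also applies to a mean difference, and the plan reports medians, so the shifts are indicative. The Wilcoxon comparison with baseline is a before-after test, and equal sequences would not remove time trends from it.

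The shift is a fraction of an unknown. No period effect in sputum glucose is given, the remark about winter concerns exacerbations, and recruitment over 12 months (section 10.2) partly spreads season over both periods. This stands and keeps the severity modest. So does the fact that 73% of randomisations give 23:17 or better.

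Finally, simple randomisation does have a benefit, since the next allocation is wholly unpredictable. Section 2.1 lists gastrointestinal effects as very common, which may partly unblind, and under sections 7.1.1 and 7.2 the same investigator confirms eligibility and takes consent. The risk from blocking is small but not nil.

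**Conclusion.** The point holds as a modest one. The plan guards against a period effect neither by design nor by analysis, and there is about a one in four chance of a split at which at least 20% of any such effect enters the unadjusted mean difference. The imbalance figures are exact, given 1:1 allocation. The shifts in µM rest wholly on the assumed period effect, and with no period effect there is no shift. The main consequence is a pilot estimate that could mislead the planning of a later trial. The documents do not support calling the design invalid, the estimate biased on average, or the planned test prone to false positives.

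**What to change.** Replace the text of section 7.3 with: participants are allocated 1:1 to the two treatment sequences by permuted blocks of randomly varying size, with block sizes withheld from site staff. For illustration, blocks of 4 would give exactly 20:20 at full recruitment and never a difference above 2.

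Pair this with a change to section 10.3.2: a within-person comparison of metformin with placebo that adjusts for period. A rank-based form is available: calculate each person's period 1 minus period 2 difference and compare these differences between sequences with a Mann-Whitney test. The treatment effect is then half the between-sequence shift.

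Both parts are needed. Withdrawals and the protocol-compliant population in section 10.7 can unbalance the sequences again, and blocking alone only halves the root-mean-square leak among 30 completers (about 18% to 9%). The period term removes it, and blocking then avoids the small loss of precision.

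The cost is one sentence on allocation, a revised analysis paragraph, and confirmation that INFORM can run such a list (the protocol only names the system), all before the first randomisation. Allocation becomes slightly more predictable, which blinding and varying block sizes largely offset.

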7.3.1 Method of implementing the randomisation/allocation sequence

The randomisation will be carried out using INFORM.

7.4

Blinding

The trial participants, care providers and outcome assessors will all be blinded. Randomisation will be the responsibility of the trial statistician and the medication will be dispensed in a blinded fashion from the hospital pharmacy. The trial medication will be over encapsulated. The final unblinding of all trial participants will occur at the end of the study after a close out visit and the creation of a locked analysis dataset.

7.5 Emergency Unblinding

The trial code will only be broken for valid medical or safety reasons e.g. in the case of a serious adverse event where it is necessary for the investigator or treating health care professional to know which treatment the patient is receiving before the participant can be treated. This will be will be carried out using INFORM.

7.6 Baseline data

Baseline data collected will include:

- 1) Demographic data
- 2) Blood tests (full blood count, blood glucose, renal function, liver function tests)
- 3) Lung function
- 4) Sputum samples (either spontaneous or induced)
- 5) Nasal SAM strips
- 6) Quality of life/symptom scores

7.7 Trial assessments

After baseline assessment, participants will either be commenced on metformin or placebo for 3 months during which time the participants will have monthly visits. At these visits the following assessments will be carried out:

- 1) Collection of data regarding exacerbations and adverse events
- 2) Physical examination
- 3) Blood tests (renal function, liver function tests)
- 4) Lung function
- 5) Sputum samples collected (either spontaneous or induced)
- 6) Nasal SAM strips
- 7) Quality of life/symptom scores

Following a 2 week washout period the subjects will crossover to the other study arm for another 3 months and follow the same study protocol.

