3.3 Outcome measures/endpoints

3.4 Primary endpoint/outcome

The median concentration of glucose in sputum in COPD patients after 3 months treatment with metformin compared with 3 months of placebo.

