4 TRIAL DESIGN

The proposed study will be a randomised, double-blinded, placebo-controlled, cross-over study of metformin in patients between the ages of 40 and 75 with a confirmed diagnosis of COPD. It will be an exploratory pilot trial, to gather preliminary information on the effects of metformin on sputum glucose and the feasibility of conducting a full-scale trial.

All subjects will have clinical assessments and blood, airway samples (nasal SAM and sputum) collected at baseline prior to the treatment phase. Clinical assessments will include lung function (FEV₁ and FVC), quality of life and symptom questionnaires (St George's Respiratory Questionnaire, COPD assessment test). Subjects will then either be commenced on metformin or placebo for a period of 3 months and blood, sputum and nasal samples collected at monthly intervals. Following a 2 week washout period the subjects will crossover to the other study arm for another 3 months and repeat samples collected.

Primary Outcome

The primary outcome will be sputum glucose measured using an enzymatic assay (AmplexRed® – ThermoFisher) after 3 months treatment with metformin. There is currently no data on which to base a power calculation and therefore this pilot study will assess what the size of any effect of metformin is in COPD subjects and thereby provide data that can be used to power any future, larger clinical trials.

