10.8 Procedure(s) to account for missing or spurious data

As the study is a small single-centre pilot study with a single primary outcome measure we do not expect missing or spurious data.

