16.4 Appendix 2 – Schedule of Procedures

Procedures	Visits								
	Screening	Baseline	Treatment Phase						
			Arm 1			Arm 2			
			1 month	2 months	3 months	Baseline	1 month	2 months	3 months
Informed consent	x								
Demographics	x								
Medical history	x								
Physical examination	x	x	x	x	x	x	x	x	x
Vital signs	x	x	x	x	x	x	x	x	x
Concomitant medications	x	x	x	x	x	x	x	x	x
ECG	x								
Laboratory tests	x	x	x	x	x	x	x	x	x
Eligibility assessment	x								
Randomisation		x							
Dispensing of trial drugs		x	x	x		x	x	x	
Compliance		x	x	x	x	x	x	x	x
Blood test		x	x	x	x	x	x	x	x
Sputum sample		x	x	x	x	x	x	x	x
Nasal SAM		x	x	x	x	x	x	x	x
Lung function		x	x	x	x	x	x	x	x
SGRQ		x	x	x	x	x	x	x	x
CAT		x	x	x	x			x	x
Adverse event assessments			x	x	x			x	x

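### Sputum is collected at months 1, 2 and 3 of both periods, but the primary analysis is an unpaired month-3 comparison with no role for months 1 and 2 and no provision for missing samples; a crossover mixed model is a cheap improvement

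*Combined protocol and SAP*

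**What the plan says.** Section 4 has "blood, sputum and nasal samples collected at monthly intervals" in the first period. Section 7.7 includes "Sputum samples collected (either spontaneous or induced" in the monthly visit list and says that participants then "crossover to the other study arm for another 3 months and follow the same study protocol". In the schedule of procedures (Appendix 2), the "Sputum sample" row is marked at baseline and at months 1, 2 and 3 of each arm.

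The primary endpoint in section 3.4 is "The median concentration of glucose in sputum in COPD patients after 3 months treatment with metformin compared with 3 months of placebo". The table in section 3.7 gives 3 months as the only time point. Section 10.3.2 says that the endpoint "will be analysed using a Mann-Whitney test", treated against non-treated. It adds a Wilcoxon matched-pairs test of post-treatment against baseline values, without restating the time point. Section 10.3.3 applies the same approach to secondary outcomes, and section 3.6 lists no exploratory endpoints.

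On missing data, section 10.8 says "we do not expect missing or spurious data". Section 10.1 sets the requirement at 30 participants and recruits 40 to cover withdrawals. Section 10.7 limits the analysis to a protocol-compliant population.

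**The concern.** Each participant gives six on-treatment sputum samples. Four of them, at months 1 and 2 of each period, have no stated part in any glucose analysis. The test for the remaining two ignores that both come from the same person, and it has no period term. Nothing is said about a participant who lacks a month-3 sample, and section 10.7 could be read as removing that person altogether.

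The trial exists to estimate an effect size for a larger study (section 4). What is at stake is the precision of that estimate and how far it depends on who happens to complete both periods.

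**Working it through.** **The plan's own figures.** The plan gives no figure for the value of the monthly samples. The one relevant figure is the withdrawal allowance: 30/40 = 75% retained, so 25% loss is provided for. This sits beside the expectation of no missing data in section 10.8.

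**Sample count.** 3 months × 2 periods = 6 on-treatment samples per participant. The endpoint uses 2 and leaves 4. For 40 completers that is 240 samples, 80 of them at month 3 and 160 at months 1-2.

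**Assumed inputs (not in the documents).** 36 participants in equal sequences. On log glucose: between-person variance b = 0.30, person-by-period variance 0.05-0.15, visit variance 0.15-0.25. The within-person variance of one value, w, is the sum of the last two: 0.20 to 0.40.

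**Step 1, pairing.** With n participants, the paired month-3 difference has variance 2w/n. An unpaired comparison works with 2(b + w)/n. The ratio is w/(b + w).
- w = 0.20: 0.20/0.50 = 0.40, so 60% lower.
- w = 0.40: 0.40/0.70 = 0.57, so 43% lower.

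This is a normal-theory analogue of the rank test, hence roughly 40-60%.

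**Step 2, complete data.** With treatment-by-month terms and equal sequences, the month-3 contrast has the same variance with or without months 1-2 (ratio 1.000). Earlier visits then add nothing to it. If simple randomisation left the sequences unequal, they could add a little through the shared period effect.

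**Step 3, samples missing at random with probability m.** Complete month-3 pairs number n(1 − m)². Participants with only one month-3 value number 2nm(1 − m). A month-3-only mixed model keeps these single values and multiplies the information from complete pairs by 1 + [2m/(1 − m)] × w/[2(b + w)].
- m = 5%: 1 + 0.105 × (0.20 to 0.286) = 1.021 to 1.030, so 2-3% lower variance.
- m = 25%: 1 + 0.667 × (0.20 to 0.286) = 1.133 to 1.190, so 12-16% lower variance.

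Generalised least squares with all visits gives a total of about 5-32% below complete pairs across m = 5-25%. Months 1-2 account for about 2-19% over the month-3-only mixed model.

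**Step 4, withdrawal.** Suppose 5-25% of participants withdraw, each at one of the six visits with equal chance, and lose every later visit. All of them lose the last month-3 value; half keep the first. At 25%, single values per pair are 0.125/0.75 = 0.167, so the month-3-only model gains a factor of 1.033 to 1.048 (3-5% lower variance). With all visits the total is about 1-10% across 5-25% withdrawal, and months 1-2 add up to about 6%.

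The upper ends in steps 3 and 4 depend a little on the approximation. Averaging information over the missing-data patterns gives 29% and 17% in step 3, and about 9% and 5% in step 4.

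**Step 5, why the three-month average is only supportive.** If monthly treatment differences correlate at r, averaging multiplies the variance by (1 + 2r)/3. Take 733 µM as the SD of the difference (an assumption) and 0.30 × 1,007 = 302.1 µM as the effect. A paired t-test of month 3 at n = 30 then has 59% power.
- Constant effect: the average has 85%, 76%, 68% and 62% power for r = 0.3, 0.5, 0.7 and 0.9.
- Effect at half strength in month 1 and 80% in month 2: the mean reduction is 30 × (0.5 + 0.8 + 1)/3 = 23%, and power is 63%, 54%, 47% and 41%. Averaging then loses power at r of 0.5 or more.

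Section 8.6 places dose escalation in month 1, so a build-up cannot be ruled out.

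**The case against.** A single fixed time point is a legitimate choice for an exploratory pilot, and month 3 is the declared endpoint. A reader might infer that the plan throws away two thirds of its primary data. The documents do not support that. Months 1-2 are not primary-endpoint data, two thirds is a count of samples and not of information, and step 2 shows no gain for month 3 when nothing is missing.

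Nor do the documents say that glucose is measured monthly. Section 7.7 speaks of collection, section 4 ties the assay to 3 months of treatment, section 7.2.1 banks unused samples, and sputum also serves culture and inflammatory markers. So the change cannot be called free.

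It is also tempting to say that one missed month-3 sample costs the plan a pair. The Mann-Whitney test forms no pairs and would keep the other value, unless section 10.7 removes the participant. Complete pairs are therefore a benchmark for a sound crossover analysis and not the written plan. Part of the gain against that benchmark, often about half, comes from keeping single month-3 values and not from months 1-2.

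Finally, withdrawal is the only loss that the protocol anticipates, and under withdrawal the gain is small. All of these points stand. They limit the size of the benefit, but they do not defend an unpaired test or the absence of a missing-data rule.

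**Conclusion.** The point holds as a cheap improvement. The plan collects monthly sputum in both periods, analyses month 3 without pairing, gives months 1-2 no glucose analysis, and makes no provision for the losses that it recruits against.

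The larger benefit comes from using the within-person design. Months 1-2 are a modest extra: nothing for month 3 with complete data, a few per cent under withdrawal, and at most about 19% if a quarter of samples vanish at random. The mixed model also rests on a weaker missing-data assumption than complete pairs, because loss may depend on values already observed. The direction is secure; the sizes depend on variances and missingness rates that the documents do not give.

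**What to change.** In section 10.3.2, replace the Mann-Whitney test with a linear mixed model on log sputum glucose at months 1-3 of both periods: fixed effects for treatment, period, month and treatment-by-month; random effects for participant and participant-by-period. The primary result is the month-3 metformin/placebo ratio with its 95% confidence interval. If glucose is roughly lognormal, this is a ratio of medians and so stays close to the stated endpoint. Report the months 1-3 average as supportive only.

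State whether month-1 and month-2 glucose is assayed. Replace the statement in section 10.8 with the missing-data assumption of the model, and word section 10.7 so that participants with incomplete data stay in.

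Cost: SAP text, somewhat more programming, a model assumption on the log scale that needs a residual check and, if months 1-2 are not already assayed, up to 4 × 40 = 160 further glucose assays on samples already collected. No visit or procedure is added.
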